2. TRIAL OBJECTIVES AND ENDPOINTS

Objectives and Endpoints:		
	Objectives	Endpoints
Part 1: Dose Optimization		
Primary	To identify a clinically active and tolerable systemic exposure range of bezuclastinib in subjects with AdvSM	
 Safety assessments (incidence of adverse events [AEs], serious adverse events [SAEs], changes from baseline in laboratory results) and dose modifications Pharmacokinetics (PK) and pharmacodynamic assessments Overall response rate (ORR) based on the modified IWG-MRT-ECNM response criteria per Central Response Review Committee (CRRC)
Part 2 Stage 1: Dose Confirmation		
Primary	To confirm the optimal dose of bezuclastinib in subjects with AdvSM	
 Safety assessments (incidence of AEs, SAEs, changes from baseline in laboratory results) and dose modifications PK and pharmacodynamic assessments ORR based on the modified IWG-MRT-ECNM response criteria per Central Response Review Committee (CRRC)
Part 2 Stage 2: Expansion		
Primary	To determine the efficacy of bezuclastinib at the selected optimal dose in subjects with AdvSM who are evaluable based on the modified IWG-MRT-ECNM response criteria	ORR defined as the percentage of subjects classified as confirmed responders (complete response [CR], CR with incomplete hematologic recovery [CRh], partial response [PR], and clinical improvement [CI]) according to modified IWG-MRT-ECNM response criteria as assessed by CRRC
Part 1 and Part 2		
Secondary	To characterize the safety and tolerability of bezuclastinib in subjects with AdvSM	Incidence of AEs, SAEs, AEs leading to dose modifications, and changes from baseline in laboratory results
	To evaluate additional efficacy parameters with bezuclastinib in subjects with AdvSM	Duration of response (DOR), defined as the date of the first documented response (CR, CRh, PR, or CI) to date of first documented disease progression or loss of response, or death from any cause, whichever occurs first, based on modified IWG-MRT-ECNM response criteria
		Time to response (TTR), defined as the date of randomization/first dose of study drug to the date of the first documented response (CR, CRh, PR, or CI) based on modified IWG-MRT-ECNM response criteria
		Progression-free survival (PFS), defined as the date of randomization/first dose of study drug to the date

Objectives and Endpoints:		
	Objectives	Endpoints
		of first documented disease progression, or death from any cause, whichever occurs first
		Overall survival (OS), defined as the date of randomization/first dose of study drug to the date of death from any cause
		Pure Pathologic Response (PPR), including complete remission, complete remission with partial hematologic recovery, molecular complete remission, and partial remission (Gotlib et al, 2020)
		Changes in spleen and liver size assessed by magnetic resonance imaging (MRI)
	To determine the effects of bezuclastinib on serum tryptase	Changes in the levels of serum tryptase
	To determine the effects of bezuclastinib on KIT D816V mutation allele burden	Changes in the levels of KIT D816V mutation allele burden in blood and bone marrow
	To evaluate histopathologic response in the blood and bone marrow	Change in pathologic findings in the blood and bone marrow, including mast cell infiltration, monocytosis, and eosinophilia
	To assess the PK of bezuclastinib in subjects with AdvSM	Plasma concentrations and PK parameters (eg, area under the plasma concentration-time curve [AUC] and maximum observed plasma concentration [C _{max}]) of bezuclastinib
	To assess patient-reported outcomes in subjects with AdvSM	Patient Global Impression of Change (PGIC) scale and change and percent change from baseline in the following patient-reported outcome measures: Patient Global Impression of Severity (PGIS) scale, Mastocytosis Quality of Life Questionnaire (MC-QoL), and Mastocytosis Activity Score (MAS) where appropriate translations are available (Siebenhaar et al, 2018; Siebenhaar et al, 2016)
	To explore the effect of bezuclastinib in subjects with AdvSM who are non-evaluable based on the modified IWG-MRT-ECNM response criteria	
 • Incidence of AEs, SAEs, AEs leading to dose modifications, and changes from baseline in laboratory results • PPR, including complete remission, complete remission with partial hematologic recovery, molecular complete remission, and partial remission (Gotlib et al, 2020)

Objectives and Endpoints:		
	Objectives	Endpoints
Exploratory	To explore various pharmacodynamic markers and their relationship with clinical safety and efficacy	Blood and bone marrow obtained at various timepoints throughout the trial to determine the effects of bezuclastinib on pharmacodynamic markers, including KIT D816V mutation allele burden and myeloid mutation profile as a measure of pharmacodynamic activity
	To explore the PK/pharmacodynamic relationships	Assessing the relationships between bezuclastinib PK and pharmacodynamic markers including KIT D816V mutation allele burden
	To explore changes in cutaneous lesions in subjects with baseline mastocytosis in skin	Change in number or pigmentation of cutaneous lesions by standardized photographs
	To explore changes in C-findings	Proportion of subjects with resolution of C-findings, including resolution of hypoalbuminemia and changes in size of skeletal lesions

3. INVESTIGATIONAL PLAN

3.1. STUDY DESIGN

This is a Phase 2, open-label, 2-part clinical study to evaluate the safety, efficacy, PK, and pharmacodynamics of the KIT inhibitor bezuclastinib in patients with AdvSM. Part 1 will determine a clinically active and tolerable exposure range of bezuclastinib in subjects with AdvSM using Formulation A. Part 2 will be conducted with a 2-stage design to support the introduction of Formulation B: Stage 1 will confirm the optimal dose of bezuclastinib Formulation B, and Stage 2 will consist of an expansion period.

3.1.1. Study Governance

An EC will review subject eligibility and will approve subject enrollment during the Screening Period. The clinical history and pathology must be centrally reviewed before a subject is enrolled. The EC will consist of a pathologist and at least 1 clinician who is skilled in the diagnosis and treatment of mastocytosis.

A Study Steering Committee (SSC) will be responsible for advising the Sponsor throughout Part 1 and Part 2 of the study. The SSC will be composed of Lead Principal Investigators and the Study Medical Monitor and will be responsible for assisting the Sponsor with protocol development, amendments, study conduct, and interpretation of data. The selected dose for Part 2 Stage 2 based on available data from Part 1 and Part 2 Stage 1 will be reviewed and confirmed by the SSC before the selected dose is administered in Part 2 Stage 2.

A Central Response Review Committee (CRRC) will retrospectively review disease-specific eligibility criteria and the presence of 1 or more baseline modified IWG-MRT-ECNM findings. The CRRC will review all available data to assess response per the modified IWG-MRT-ECNM response criteria. The CRRC will consist of an independent pathologist, 1 independent clinician, and at least 2 clinicians who are skilled in the treatment of mastocytosis.

An Independent Data Monitoring Committee (IDMC) will aid in the monitoring of accumulating study data to ensure the ongoing safety of trial participants and will play a role in confirming the recommendations and decisions made by the Sponsor across bezuclastinib clinical trials. The IDMC membership will be composed of external medical experts with relevant clinical experience. The IDMC will review the available data and recommendation from the SSC regarding the optimal dose selected in Part 2 Stage 1 for Part 2 Stage 2. The IDMC will have the right to recommend stopping the study at any time due to concerns for the safety of the subjects.

Charters will govern each of these committees as appropriate.

3.1.2. Part 1: Dose Optimization

In Part 1 of the study, approximately 28 subjects will be randomized to 1 of 4 dose cohorts of bezuclastinib (Formulation A), including up to 4 subjects who are non-evaluable per modified IWG-MRT-ECNM response criteria based on lack of evaluable organ damage per modified IWG-MRT-ECNM criteria. Subjects will be randomized in a 1:1:1:1 (50 mg BID:100 mg

BID:200 mg BID:400 mg QD) manner. Randomization will be stratified by evaluability per modified IWG-MRT-ECNM response criteria (ie, evaluable vs non-evaluable).

Table 4: Single-Agent Dose Optimization Cohort

	Bezuclastinib Dose × 28-Day Cycles			
	Dose Cohort 1	Dose Cohort 2	Dose Cohort 3	Dose Cohort 4
Initial Dose	50 mg BID	100 mg BID	200 mg BID	400 mg QD
Total Daily Dose	100 mg	200 mg	400 mg	400 mg

Abbreviations: BID=twice a day; QD=once daily.

Bezuclastinib Formulation A will be administered orally as a single agent and should be taken with food and water. Each 28-day period is 1 cycle. Subjects will receive bezuclastinib at their assigned dose cohort until confirmed disease progression, intolerable toxicity, Investigator decision, withdrawal of consent, or other protocol-specified reason for discontinuation of study drug, whichever occurs first. Once the optimal dose level of bezuclastinib Formulation B is confirmed in Part 2 Stage 1, subjects receiving Formulation A may be transitioned to receive Formulation B. Additional blood samples for PK may be collected following the transition from Formulation A to Formulation B.

3.1.3. Part 2: Dose Confirmation and Expansion

Part 2 will be conducted with a 2-stage design: Stage 1 will confirm the optimal dose of bezuclastinib Formulation B, and Stage 2 will consist of an expansion period.

In Stage 1, approximately 20 subjects who are evaluable per modified IWG-MRT-ECNM response criteria will be randomized 1:1 to receive 150 mg QD or 300 mg QD of bezuclastinib Formulation B. Randomization will be stratified by prior treatment of TKI (ie, yes vs no). Based on available data from Part 1, 150 mg QD of bezuclastinib Formulation B is expected to provide clinical activity with acceptable safety and tolerability. A higher dose level of bezuclastinib, 300 mg QD, will also be explored to determine if an increased dose results in increased clinical activity with acceptable safety and tolerability. The totality of clinical data from Part 1 and Part 2 Stage 1 will be used to confirm the optimal Formulation B dose of bezuclastinib in subjects with AdvSM. Subjects in Part 2 Stage 1 may have their dose adjusted once the optimal dose of bezuclastinib Formulation B is confirmed.

Once approximately 20 subjects have been enrolled in Part 2 Stage 1, enrollment may continue until the dose for Part 2 Stage 2 is confirmed. Following enrollment of 20 subjects in Part 2 Stage 1 and prior to analysis of Part 2 Stage 2 data, enrolled subjects will receive either 150 mg and/or 300 mg based on ongoing review of available data and following IDMC approval. Of the additional subjects who may be enrolled, those who receive the dose selected for Part 2 Stage 2 will contribute to the Stage 2 analysis population.

In Stage 2, approximately 55 subjects who are evaluable per modified IWG-MRT-ECNM response criteria will be enrolled to receive bezuclastinib Formulation B at the selected optimal

dose. Up to approximately 15 additional subjects who are non-evaluable per modified IWG-MRT-ECNM response criteria based on lack of evaluable organ damage per modified IWG-MRT-ECNM criteria may be enrolled.

To ensure the study population reflects the general AdvSM patient population, enrollment of the SM-AHN subtype will be capped at approximately 80% ([Jawhar et al, 2019](#)).

Bezuclastinib will be administered orally as a single agent. Each 28-day period is 1 cycle. Subjects will receive bezuclastinib at the selected Part 2 dose until confirmed disease progression, intolerable toxicity, Investigator decision, withdrawal of consent, or other protocol-specified reason for discontinuation of study drug ([Section 4.3.1](#)).

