8. STATISTICAL METHODS AND DATA ANALYSIS

8.1. GENERAL STATISTICAL CONSIDERATIONS

A detailed statistical analysis plan (SAP) will be finalized before database lock and will document the analysis methods, data handling procedures, the handling of missing data, and other statistical analysis issues. Statistical analyses will be performed using SAS® software version 9.4 or higher. Data for Part 1, Part 2 Stage 1, and Part 2 Stage 2 will be analyzed separately.

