8.2. DETERMINATION OF SAMPLE SIZE

Approximately 28 subjects will be randomized 1:1:1:1 into 4 dose cohorts (Formulation A) in Part 1, including up to 4 subjects who are non-evaluable per modified IWG-MRT-ECNM response criteria based on lack of evaluable organ damage per modified IWG-MRT-ECNM criteria. It was determined that approximately 6 subjects evaluable per modified IWG-MRT-ECNM response criteria per group (24 total) would allow for ruling out an ORR of 60% or higher if a dose group had an ORR estimate of 16.7% or less (ie, if the ORR for a dose is 1/6, the upper bound of the 1-sided 90% confidence interval is 51.0% via a Clopper-Pearson exact confidence interval). Dose decisions will be based on an assessment of safety, biomarker, and clinical efficacy, and PK endpoints at each dose, with summary statistics and figures being used to illustrate dose-response.

Part 2 of the study will enroll approximately 75 subjects who are evaluable per modified IWG-MRT-ECNM criteria and up to an additional 15 subjects with AdvSM who are non-evaluable per modified IWG-MRT-ECNM response criteria at study entry.

For Part 2 Stage 1, approximately 20 subjects who are evaluable per modified IWG-MRT-ECNM will be randomized in a 1:1 ratio to receive bezuclastinib 150 mg QD or 300 mg QD (Formulation B). It was determined that approximately 10 subjects evaluable per modified IWG-MRT-ECNM response criteria per group would allow for ruling out an ORR of 60% or higher if a dose group had an ORR estimate of 30.0% or less (ie, if the ORR for a dose is 3/10, the upper bound of the 1-sided 90% confidence interval is 55.2% via a Clopper-Pearson exact confidence interval). The determination of the optimal dose will be based on totality of the data including assessment of safety, biomarker and clinical efficacy, and PK endpoints at each dose level.

For Part 2 Stage 2, approximately 55 subjects who are evaluable per modified IWG-MRT-ECNM response criteria will be enrolled. The null hypothesis is that ORR for subjects who received bezuclastinib treatment will be the same as the historical control (28%) (RYDAPT SmPC, 2021). Assuming the ORR for subjects who received bezuclastinib is 60%, 55 evaluable subjects will provide at least 90% power to reject the null hypothesis based on a Chi square test at one-sided alpha of 0.025.

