8.7. EFFICACY ANALYSES

The primary efficacy endpoint for subjects who are evaluable per modified IWG-MRT-ECNM response criteria is ORR, defined as the percentage of subjects classified as confirmed responders (CR, CRh, PR, or CI) according to the response assessment based on modified IWG-MRT-ECNM response criteria by CRRC assessment (see [Table 8](#)). Analysis of the primary efficacy endpoint will be performed on the ITT Analysis Set for Part 1, Part 2 Stage 1, and Part 2 Stage 2, separately. For the purposes of dose selection, subjects who had dose reductions will be treated as non-responders for their assigned dose arm as a sensitivity analysis. For each dose

group, summary statistics including the number and proportion of confirmed responders with 95% confidence intervals will be presented.

Other efficacy assessments include DOR, TTR, and PFS, based on modified IWG-MRT-ECNM, PPR, and OS. The endpoints based on modified IWG-MRT-ECNM response criteria will be summarized using the ITT Analysis Set. Sensitivity analysis for selected efficacy endpoint will be summarized using the mITT analysis set.

All efficacy endpoints will be summarized by study part/stage (Part 1, Part 2 Stage 1, and Part 2 Stage 2) and dose cohort. Efficacy endpoints will be listed as well. When appropriate, subjects across study parts and by disease subtype may also be grouped.

Table 8: Response Category for Responder Definition by Subject Type

Responder	Modified IWG-MRT-ECNM Criteria
Yes	Complete Remission (CR)
	Complete Remission with Incomplete Hematologic Recovery (CRh)
	Partial Remission (PR)
	Clinical Improvement (CI)
No	Stable Disease (SD)
	Progressive Disease
	Loss of Response
	Not Evaluable

Source: [Gotlib et al, 2013](#).

The summaries for the following endpoints will be provided along with 95% confidence intervals. Individual subject responses will also be represented using waterfall plots.

- Number (%) of subjects in each tumor response category
- Number (%) of subjects who met the Overall Responder definition (CR+CRh+PR+CI)
- Number (%) of subjects who met the Complete Remission criteria (CR+CRh)
- Number (%) of subjects who met the criteria for PPR

For Part 2 Stage 2, ORR will be tested against null hypothesis of response rate 0.28 using Chi square test at one-sided alpha of 0.025.

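### Subjects dosed before dose confirmation enter the Stage 2 test only if their dose is selected, and the protocol does not keep their responses out of that selection

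*Protocol*

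**What the plan says.** Protocol Section 3.1.3 (repeated in the Synopsis and Section 8.2) describes three groups in Part 2.

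- Stage 1: "approximately 20 subjects who are evaluable per modified IWG-MRT-ECNM response criteria will be randomized 1:1" to 150 mg QD or 300 mg QD.
- Overflow: once about 20 are in, "enrollment may continue until the dose for Part 2 Stage 2 is confirmed". These subjects receive either or both doses according to an ongoing review of the data and with IDMC approval. Of them, "those who receive the dose selected for Part 2 Stage 2 will contribute to the Stage 2 analysis population".
- Stage 2: about 55 evaluable subjects at the selected dose.

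Section 8.7 gives the test for Stage 2: "ORR will be tested against null hypothesis of response rate 0.28 using Chi square test at one-sided alpha of 0.025". Section 8.3 plans no multiplicity adjustment.

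On the data behind the dose choice, the sections differ. The Synopsis (Study Design and Methodology) has the SSC and sponsor review all available data, efficacy included, after all Stage 1 subjects have completed at least 2 cycles. Section 1.3.3 places the decision after approximately 20 subjects have completed at least 2 cycles. Section 3.1.1 refers to available data from Part 1 and Part 2 Stage 1. Section 8.2 lists clinical efficacy with safety, biomarker and PK data as grounds for the choice. No section states whether overflow subjects' efficacy data belong to that review.

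**The concern.** An overflow subject's place in the Stage 2 test depends on which dose wins. If that subject's response also helped to decide which dose wins, the same observation is used to select and then to test. Overflow subjects at the selected dose would on average look better than the dose truly is, because a dose with a lucky run is more likely to be chosen. Those at the other dose leave the test. The study is open-label, and no cutoff, allocation rule, firewall or adjustment is stated for these subjects. At stake are the Stage 2 ORR estimate and the false-positive rate of the only formal test in the trial.

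**Working it through.** **Inputs from the protocol.** Null ORR 0.28, alternative 0.60, N = 55, one-sided alpha 0.025 (Sections 8.2 and 8.7); about 10 randomised subjects per dose in Stage 1 (Section 3.1.3).

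**Assumption.** m overflow subjects per dose. The protocol gives no number, so a range is shown.

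**The plan's own figure.** Section 8.2: "Assuming the ORR for subjects who received bezuclastinib is 60%, 55 evaluable subjects will provide at least 90% power to reject the null hypothesis". The one-sample chi-square (score) statistic is z = (x/55 − 0.28) / √(0.28 × 0.72 / 55).

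- x = 21 gives z = 1.68; x = 22 gives z = 1.98. The cutoff is therefore 22 of 55.
- Power: P(X ≥ 22 | 55, 0.60) = 0.999. The stated floor of 90% is met.
- Actual size with no selection: P(X ≥ 22 | 55, 0.28) = 0.037. An exact test needs 23 of 55 and has size 0.019.

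**Selection model.** Both doses have the same true ORR. Each has 10 Stage 1 plus m overflow subjects. The dose with more responders is selected, with ties broken at random. Its m overflow subjects are pooled with 55 − m new subjects and tested.

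Results at a true ORR of 28%:

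| m per dose | Rise in tested ORR (points) | Type I error, chi-square (≥22/55) | Type I error, exact (≥23/55) |
|---|---|---|---|
| 0 | 0 | 0.037 | 0.019 |
| 5 | 0.6 | 0.045 | 0.024 |
| 10 | 1.0 | 0.050 | 0.027 |
| 20 | 1.7 | 0.058 | 0.031 |

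Link between overflow and tested ORR at m = 10: overflow subjects on the winning dose average 33.6%, so the tested ORR rises by (10/55) × (33.6 − 28.0) = 1.0 point.

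**Variants.**

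- Choice made on the 20 randomised subjects alone: bias 0 and type I error unchanged, for every m.
- Only half of eventual responses known at selection, m = 10: +0.6 points; type I error 0.045 (chi-square) and 0.024 (exact).
- True ORR 60%: bias of +0.6 to +1.8 points for m = 5 to 20, with power at 0.999 or above.

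**Against planned size.** Part 2 is planned at about 20 + 55 = 75 evaluable subjects. Winning-dose overflow fits inside the 55; losing-dose overflow is extra. So m = 5, 10 and 20 imply 80, 85 and 95 evaluable subjects.

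**The case against.** The strongest reply is that no section says overflow responses inform the choice. Section 1.3.3 points to about 20 subjects, and on that reading there is no bias. This stands, and it is why the point is conditional. But the Synopsis reading is equally open, particularly if overflow subjects count as Stage 1 subjects, and the validity of the test should not turn on which section one follows.

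Second, timing and criteria weaken the mechanism. Section 8.4.4 puts the minimum follow-up for a confirmed response at 20 weeks, whereas 2 cycles are 8 weeks, and the choice also weighs safety, biomarker and PK data. A choice driven by tolerability need not raise ORR. This too stands; the table is near the worst case. It does not remove the concern, because Section 3.1.4 schedules a marrow assessment at Cycle 3 Day 1 to document initial response, and two cycles is a minimum.

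Third, the larger values of m exceed the planned Part 2 total, and much of the excess over 0.025 comes from the uncorrected chi-square, whose size is 0.037 with no selection at all. Both are correct. At m = 5 an exact test stays just under 0.025.

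Three stronger readings may tempt a reader, and the document does not support them:

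- That the inclusion rule contradicts Section 8.1, "Data for Part 1, Part 2 Stage 1, and Part 2 Stage 2 will be analyzed separately". It can be read as assigning overflow subjects to Stage 2 instead of counting anyone twice; the 20 randomised subjects stay in Stage 1.
- That it contradicts Section 3.1.1, under which the selected dose "will be reviewed and confirmed by the SSC before the selected dose is administered in Part 2 Stage 2". That sentence governs dosing within Stage 2; overflow subjects are dosed earlier, with IDMC approval.
- That overflow subjects on the unselected dose fall out of every efficacy set. The Response-Evaluable set in Section 8.4.4 does not require randomisation. What is true is narrower: if they are not randomised, Section 8.4.2 gives them no clear ITT set.

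**Conclusion.** The point holds in conditional form. The protocol admits pre-confirmation subjects to its only hypothesis test according to which dose wins, and does not say whether their responses may influence that outcome. If they do, and selection is on response alone between two equally effective doses, the tested ORR rises by about 0.6 to 1.7 points for m = 5 to 20 per dose. Type I error rises by about 0.8 to 2.1 percentage points for the chi-square test and 0.5 to 1.2 for an exact test. These sizes rest on an assumed m and on final responses being known at selection, so they lie near the upper end. It would be wrong to infer that the Stage 2 ORR is certainly biased, or that a true ORR of 60% would be put in doubt. The matter deserves correction because it touches the one confirmatory test and costs little to settle.

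**What to change.** Choose one of two wordings for Sections 3.1.3 and 8.2 and the Synopsis:

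1. Define the primary Stage 2 test population as evaluable subjects first dosed after dose confirmation, and report overflow subjects at the selected dose in a supportive pooled analysis.
2. Keep overflow subjects in the Stage 2 test, and state that their efficacy data are not used in dose selection. Safety review is unaffected.

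In either case, reconcile the Synopsis and Section 1.3.3 on whose data the dose decision uses, and bring Sections 3.1.3 and 8.2 into line. State which ITT set holds non-randomised overflow subjects on the unselected dose.

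The second option costs only wording. The first leaves somewhat fewer subjects in the primary test. Even without replacing them, exact power at 60% against 28% is 98.1% with 40 subjects (cutoff 18) and 97.0% with 35 (cutoff 16), both above the stated 90%.
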